7.7.2.2 Pooled adverse events

Adverse events will be analyzed according to four main categories:

- Proportion of subjects with *any ocular adverse event*
- Proportion of subjects with *any serious ocular adverse event*
- Proportion of subjects with *any non-ocular serious adverse event*
- Proportion of subjects with *any non-ocular adverse event*

The proportion of subjects with these events will be compared between the arms using Fisher's Exact Test. Poisson regression will be applied to compare the rates of overall adverse events, including recurrent events.

8 Reporting conventions

- All tables and data listings will be presented in landscape orientation, unless presented as part of the text of the final report.
- Figures will be presented in landscape orientation, unless the information is substantially easier to interpret in portrait orientation.
- Direct annotation of figures will be preferred to legends. All figures with more than one variable or item will contain either direct annotation or legends. All annotation will be unambiguously identifiable as such.
- Color will be used in figures only when needed to enhance clarity of communication. All color schemes will be evaluated for visual clarity for individuals with diminished color vision. All color encodings will be identified. Redundant encodings (such as the use of different plot symbols or line dash patterns) will be used in addition to color, so that all figures are interpretable after monochrome reproduction at 100 dots per inch. All dash patterns and line widths will be adequate to be distinguishable after monochrome reproduction at 100 dots per inch. Any distinction between plot symbols (circles, filled circles, diamonds, etc.) will remain clear after monochrome reproduction at 100 dots per inch.

- Sans serif fonts will be used for all labeling (Helvetica, Arial, Futura, or Computer Modern Sans Serif (CMSS)).
- Boldface and italics will not be used unless substantial value is added.
- Decorative fonts and enhancements, including borders and shading, will not be used. Decorative presentation methods, such as ribbon graphs, will never be used.
- All information given in figures will also be presented in summary tables (perhaps only included in an Appendix or in supplementary materials).
- Only standard characters will be used in tables and data listings.
- All titles will be centered. The first title line will be the number of the table, figure, or listing. The second and possibly third lines will be the description of the table, figure, or data listing. The ICH numbering convention will be used for all.
- All footnotes will be left justified and at the page bottom. Footnotes will be used sparingly. Reference footnotes will be complete enough to locate any reference based on the information provided (Author, Journal, Pages, Date, or PubMed accession number).
- Missing values for numeric or character variables will be unambiguously identified as such using the special string NA (not available) in all settings; NA is the standard missing value code for our software. Each figure or table caption in which NA is used will indicate the meaning of NA in that figure or table. The abbreviation NA will never be used for any other purpose.
- All date values will presented in the form DDmmmYYYY format (e.g. 01jan2008), using four digit years. June will be encoded as jne (otherwise jan and jun would differ by only a single character), and July as jly (so that the lowercase letter l, easily confused with the digit 1, will not be adjacent to any numerals).
- All tables, figures, and data listings will have the name of the program and a date/time stamp on the bottom of the output.

9 Abbreviations and acronyms

AES Advanced Encryption Standard

AOSLO Adaptive Optics Scanning Laser Ophthalmoscope

BCVA, BSCVA Best spectacle-corrected visual acuity

CAR(1) continuous autoregression process of order 1 (Ornstein-Uhlenbeck process)

CNTF Ciliary Neurotrophic Factor

CNTF Implant Trial The trial discussed in this SAP; official title: *Photoreceptor Structure in a Phase 2 Study of Encapsulated Human NTC-201 Cell Implants Releasing Ciliary Neurotrophic Factor (CNTF) for Participants with Retinitis Pigmentosa Using Rates of Change in Cone Spacing and Density as the Primary Outcome*

DSMC Data and Safety Monitoring Committee

ERG Electroretinography

ETDRS Early Treatment of Diabetic Retinopathy Study

FDA U.S. Food and Drug Administration

FIPS Federal Information Processing Standard

JD [name]

NIST National Institute of Standards and Technology

PI Principal Investigator

ROI region of interest

SAP Statistical Analysis Plan

SMC Safety Monitoring Committee

TP [name]

UCSF University of California, San Francisco

References

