3.3 Randomization

Each patient will receive a unique identifier. Each patient will be randomized to receive the implant in the right or left eye (with the sham in the other eye). [name] will generate the randomization list using the statistical package R, creating an Excel® spreadsheet in which each unique identifier is listed on a row next to a treatment assignment. The name of the file will clearly identify it as a randomization list. TP will maintain a hard copy of the randomization list in a locked cabinet in a locked room, and will communicate the randomization lists to the Study Surgeon in person (or using secure encrypted email if absolutely necessary). To ensure against

information loss due to unforeseen circumstances, a backup copy of the randomization list will be maintained by the Safety Monitoring Committee Chair in a locked cabinet stored away from the main UCSF site, and also a backup copy of the randomization list will be maintained on an encrypted partition on the REDCap server; these copies would not be accessible to the PI or to any study personnel. Our procedures are designed to maintain absolute confidentiality of the list while ensuring integrity.

The randomization protocol is as follows. First, a seed integer for the random number generator will be chosen prior to any collection of data; the choice of the seed is arbitrary, but it determines the pseudorandom sequence generated by the algorithm, and it will be recorded in a sealed envelope and kept confidential. The algorithm will be the default algorithm used by the R statistics package. Ten assignments for the right eye and ten for the left eye will then be produced by randomly shuffling a sequence of ten “R” and ten “L” characters using the `sample` command from R. These assignments will be presented in a spreadsheet to the surgeon using a hand-delivered hard copy. Each line of the spreadsheet will contain a randomization code for each patient and an assignment

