7.7 Safety and tolerability

The analysis of safety in this study will include summaries of the following:

- Exposure
- Adverse events
- Adverse events and serious adverse events
- Adverse events leading to withdrawal
- Any deaths

The incidence of adverse events will be compared between treatment and sham eyes using the McNemar test.

Additional considerations are given in §7.4.

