7.7.1 Exposure

Individual eyes are assumed to have exposure to the intervention assigned to the arm they were randomized to.

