7.7.2 Adverse Events

7.7.2.1 Individual events

The proportion of subjects with at least one of the following safety-related events will be compared using Fisher's Exact Test. Non-serious adverse events (not requiring narrative form) are listed here: irritation or infection from dilation drops, bruising from blood work.

Serious ocular adverse events (which must be reported within 24 hours and which require a narrative form) are listed here: acute angle closure glaucoma precipitated by dilation, corneal abrasion after tonometry or electroretinography, risks associated with implantation surgery (cataract, retinal detachment, infection, bleeding).

In addition, we will compare the rate of each of the adverse events during the follow-up period using Poisson regression, which can take into account multiple instances of adverse events within a single subject.

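### SAP 7.7.2 tests paired eyes with Fisher's exact test although SAP 7.7 names McNemar, and tests person-level events between arms made up of the same people

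*SAP*

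**What the plan says.** SAP 3.3 randomizes each patient to have the implant in the right or the left eye, with sham surgery in the fellow eye. SAP 7.7.1 defines arms by eye: "Individual eyes are assumed to have exposure to the intervention assigned to the arm they were randomized to".

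Three places then name a test for adverse-event proportions:

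- SAP 7.7: "The incidence of adverse events will be compared between treatment and sham eyes using the McNemar test". The form of McNemar (exact, mid-p, or chi-square with or without correction) is not given.
- SAP 7.7.2.1: "The proportion of subjects with at least one of the following safety-related events will be compared using" Fisher's exact test. The list that follows mixes events of an eye ("irritation or infection from dilation drops", and serious ocular events related to examination or surgery) with one that belongs to the person, "bruising from blood work".
- SAP 7.7.2.2: "The proportion of subjects with these events will be compared between the arms using" Fisher's exact test. This covers four categories, two of them non-ocular, for example "any non-ocular serious adverse event".

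No section ranks these tests or says how a non-ocular event is assigned to an arm.

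**The concern.** Fisher's exact test assumes two independent groups. Here the two groups are the two eyes of the same people, so the same ocular table has both a paired and an unpaired planned test, and the choice between them could be made after the data are seen.

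The direction of disagreement depends on how events cluster, and both patterns are plausible. Dilation drops, tonometry, ERG and the postoperative drops (Protocol 4.6.3) reach both eyes, which favors events in both eyes; Fisher is then too conservative and loses power to show harm. Only the implant eye has a sclerotomy and a device (Protocol 4.6.1; the sham is external pressure), which favors events in the implant eye alone; Fisher can then give a smaller p-value than exact McNemar.

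The non-ocular categories raise a different problem. A systemic event cannot be assigned to one eye, so there is no between-arm contrast. A reported p = 1 could be misread as evidence of no systemic risk.

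**Working it through.** **Inputs.** The SAP states no figure for these tests, so there is none to reproduce. The number of pairs is 20 (SAP 3.1.5 and 3.3) or about 30 (Protocol 4). Alpha is 0.05 two-sided (SAP 3.1.1). Event rates and between-eye correlation are not in the documents; those below are assumed ranges.

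**Formulas.** Let b be the number of people with the event in the implant eye only, and c the number with it in the sham eye only.

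- Exact McNemar: p = 2 × P(X ≥ max(b, c)), with X binomial (b + c, 0.5).
- Mid-p: the exact p minus P(X = max(b, c)).
- Fisher: hypergeometric, on the 2×2 table of eyes treated as independent.

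**One case by hand: b = 5, c = 0, nobody affected in both eyes, 20 pairs.** Exact McNemar: 2 × 0.5⁵ = 0.0625. Mid-p: 0.0625 − 0.03125 = 0.031. Fisher (5/20 v 0/20): 2 × C(20,5)/C(40,5) = 2 × 15,504/658,008 = 0.047. The chi-square form gives 25/5 = 5.0, p = 0.025, or with continuity correction 16/5 = 3.2, p = 0.074. Naming McNemar without its form therefore leaves the result open as well.

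**P-values, 20 pairs**

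| Both eyes | Implant only | Sham only | Fisher | Exact McNemar | Mid-p |
|---|---|---|---|---|---|
| 7 | 6 | 0 | 0.113 | 0.031 | 0.016 |
| 2 | 6 | 0 | 0.065 | 0.031 | 0.016 |
| 0 | 5 | 0 | 0.047 | 0.063 | 0.031 |
| 0 | 7 | 1 | 0.044 | 0.070 | 0.039 |

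**Power and disagreement.** For eye-level rates p1 and p0 with correlation rho, P(both) = p1·p0 + rho·√[p1(1−p1)p0(1−p0)]. The other three cell probabilities follow from the margins, and all tables are enumerated from the multinomial. For 65% v 35% at rho 0.5: P(both) = 0.2275 + 0.5 × 0.2275 = 0.341, implant only 0.309, sham only 0.009.

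| Rates, rho, pairs | Fisher | Exact McNemar | Mid-p | Fisher and exact McNemar disagree at 0.05 |
|---|---|---|---|---|
| 65% v 35%, 0, 20 | 0.34 | 0.34 | 0.43 | 7%, split evenly |
| 65% v 35%, 0.5, 20 | 0.28 | 0.56 | 0.72 | 28%, McNemar alone significant |
| 30% v 5%, 0, 20 | 0.45 | 0.34 | 0.49 | 11%, nearly all Fisher alone |
| 15% v 5%, 0, 20 | 0.070 | 0.029 | 0.076 | 4%, Fisher alone |
| 65% v 35%, 0.5, 30 | 0.57 | 0.88 | 0.94 | not tabulated |
| 15% v 5%, 0, 30 | 0.093 | 0.099 | 0.178 | not tabulated |

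For 65% v 35% with 20 pairs, disagreement is 11% at rho 0.2 and 20% at rho 0.4.

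**Fisher's type I error** (35% per eye, 20 pairs) at rho −0.3, −0.2, 0, 0.2, 0.4, 0.6: 0.051, 0.041, 0.025, 0.013, 0.004, 0.001. It is conservative rather than invalid at −0.2 and above.

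**Person-level events.** If k people have a non-ocular event, the table is k/20 v k/20, for example 6/20 v 6/20. Fisher gives p = 1 for any k, and McNemar has no discordant pairs. What can be estimated is the person-level proportion: the exact 95% CI is 0–16.8% for 0/20 and 3.2–37.9% for 3/20.

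**The case against.** - **SAP 7.7.2.1 names no comparison groups.** True; reading it as eye versus eye is an inference from 7.7 and 7.7.1. That is, however, the only contrast the SAP's safety section defines, and 7.7.2.2 names the arms explicitly. The only between-person treatment difference, high- versus low-output implant, is set by enrollment order (Protocol 4), and SAP 7.7 does not refer to it, so it does not rescue Fisher.
- **Paired analyses are already planned** (McNemar in 7.7, random-effects event-rate regression in 7.5.2.7). So the authors did not overlook pairing. But these analyses sit beside the Fisher text without replacing it, and that is the conflict.
- **Little depends on these p-values.** This stands. The SAP warns against resting safety conclusions on tests (7.4, 7.5.2, 7.5.2.7), says that stopping for harm need not wait for strong evidence (6.2.3), and acknowledges low power for unlikely events (7.4).
- **The largest differences come from assumed inputs.** This also stands. At 65% v 35%, rho 0.5 is close to the maximum those margins allow: P(both) cannot exceed 0.35, so rho cannot exceed (0.35 − 0.2275)/0.2275 = 0.54. At rho 0 the two tests have equal power there, and their remaining disagreement reflects discreteness rather than ignored correlation.
- **Pairing alone does not guarantee more power.** Correct: exact McNemar loses to Fisher at 30% v 5% and, with 20 pairs, at 15% v 5%. That is a reason to state the form of McNemar, not to keep an unpaired test.

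**Conclusion.** The concern holds, and the SAP text should be corrected. For ocular events, 7.7 and 7.7.2.2 prescribe incompatible tests for the same paired proportions, and 7.7.2.1 most naturally reads the same way as 7.7.2.2. For non-ocular events, the planned between-arm test cannot carry information.

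In the cases computed with 20 pairs, Fisher and exact McNemar disagree at 0.05 in 4% to 28% of trials, depending on assumed rates and correlation. For uncommon events (15% v 5%), none of the three tests exceeds 18% power, even with 30 pairs. The size of the problem rests on those assumptions; the mismatch between test and design, and p = 1 for person-level events, do not. The primary efficacy analysis is unaffected and no stopping boundary is involved.

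**What to change.** 1. **Ocular events.** In SAP 7.7.2.1 and 7.7.2.2, replace Fisher's test with the McNemar test of 7.7, counted by eye, and state its form. Mid-p is recommended. Add a 95% CI for the paired difference, for example by Newcombe's paired method: 13/20 v 7/20 with 7 concordant gives 0.30 (0.07 to 0.48); 5/20 v 0/20 gives 0.25 (0.04 to 0.47).
2. **Non-ocular events**, including blood-draw bruising. Report person-level counts with exact 95% CIs and no between-arm test.

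Two related wording points:

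- State that the random-effects model of 7.5.2.7 governs ocular event rates, in negative binomial form if counts are overdispersed, because 7.7.2 names plain Poisson regression. This guards against eye-level overdispersion and is not a correction for pairing.
- In SAP 4.2, tabulate whole-person discontinuation by person instead of testing it between treatment groups.

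**Cost.** SAP wording only: no patients, visits or data are added, and a few p-values are dropped. At rho 0 and above, mid-p had at least Fisher's power in every case computed. At rho −0.2 it was at most 0.014 lower (50% v 20%, 20 pairs: 0.407 v 0.421). Mid-p is not strictly bounded at 5%: its maximum type I error is 0.0504 with 20 pairs and 0.049 with 30.

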- Peri-implant fibrosis, which either blocks the visual axis of the implanted eye or affects the lens or retina (minor/moderate fibrosis around the implant and/or the attachment point is an expected possibility and will be considered safe on ocular function). Attention should focus on fibrosis that may detach the retina.
- Development of choroidal neovascularization (CNV) in the implanted eye, in which case it may be considered a safety event and explant will be considered.

- Adverse events affecting ocular function, which are different from those expected in the normal course of RP or Usher Syndrome, which are thought to be potentially related to the implant.
- Local or systemic toxicities considered serious adverse events that are potentially related to the implant.

There are risks associated with the surgeries to implant and explant the device and with the sham surgery. In general, the risks of intra-ocular surgery are very small. Some side effects could occur locally in the eye and could affect the participant's vision. There may be pain or infection, a small amount of bleeding, cataract, vitritis, and/or mild astigmatism. A retinal detachment could also possibly occur. Participants may experience a transient red eye from superficial bleeding and itching or a foreign body sensation in the corner of the eye from irritation of the suture itself. These side effects are usually temporary and generally clear up in two weeks or less. In many cases, topical antibiotics and topical steroids can treat minor degrees of inflammation or infection. More serious infection or inflammation may require further surgery on the eye, likely with removal of the implant.

In addition, all adverse events will be collected regardless of severity or potential relationship to the implant, CNTF, or surgical procedure.

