Post-Op Implant Wound Care: Starting the next day, the participant will self-administer the following medications is provided in section 4.6.3

Sham Implant Surgery

1. These instructions assume that the surgeon completed the implant eye surgery first and operates on the sham eye immediately upon completion of the implant surgery.
2. If the peribulbar anesthesia was used in implant surgery, either administer the peribulbar block to the sham eye at this point using bupivacaine 0.5% with lidocaine 2% 1:1, or perform a small skin puncture using small gauge needle, to simulate the skin puncture in the fellow eye, without the actual block being placed.
3. Prep with anesthetic and iodine-based solution(s) and drape in the usual sterile fashion. For example, scrub/prep the periocular region with 10% iodophor and rinse the exposed surface of the eye and the conjunctiva with 5% iodophor solution. Note that the sham eye may be scrub prepped at the time of implant eye preparation.
4. Placing corneal shield or alternative to avoid direct illumination of the macula is recommended
5. Secure the sterile drapes.
6. Retract the eyelids with a lid speculum.
7. Perform an inferior limbal conjunctiva peritomy under microscopic visualization using scissors.
8. If a subtenon block will be used, then apply it at this point to the sham eye using bupivacaine 0.5% with lidocaine 2% 1:1 (unless the surgeon prefers the peribulbar block (see above)).
9. Apply pressure for two seconds at 3.75 mm posterior to the limbus in the inferotemporal quadrant. Select an alternative quadrant if the vitreo-retinal surgeon determines that the pressure should not be applied in the inferotemporal quadrant.
10. Close the conjunctiva with 7-0 vicryl suture.
11. Day of Surgery Wound Care Recommendations:

- a. At the end of surgery, administer subconjunctival dexamethasone (2mg/0.5 ml (4mg/ml), or comparable; *If the case is complicated and excess inflammation is anticipated in the opinion of the investigator, a higher dose of dexamethasone (0.5cc of 10mg/ml or comparable) may be used.*
- b. Apply Vigamox® (moxifloxacin) to eye prior to patching
- c. Patch eye during the post surgical observation period as deemed necessary

Post-Op Implant Wound Care: Starting the next day, the participant will self-administer the following medications is provided in section 4.6.3

12. Examine the eye will with an indirect ophthalmoscope.

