3.1 Sample Size Planning

3.1.1 Alpha level

The study hypotheses are listed as bidirectional effects; we will never conduct one sided tests. All hypothesis tests proposed for the CNTF Implant Trial are two-sided.

Results will be judged significant using a two-tailed α of 0.05.

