3.1.2 Power

We plan recruitment of sufficient subjects for an 80% power to detect an effect size of 0.084 arcminutes over two years.

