3.1.5 Sample size calculation methodology

We used a simplified version of the analysis we plan in order to estimate the power for the more complex analysis. This reduces the analysis to a paired T-test. More specifically, we determined the rate of change over time of the cone spacing in our pilot patients, and computed a pooled standard deviation over all these regions (in untreated persons) from which we derived an expected standard deviation of the difference in the total change in cone spacing after two years of approximately 0.11. Using the standard formula for the sample size of a one-sample T-test

(e.g. Chow et al, 2007, formula 3.1.2), we find we would need a total of 17 individuals per group, or 20 adjusting for loss to follow-up.

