7.5.2.7 Other outcomes

For the incidence of adverse events following application of the investigational product in all subjects, we propose to use Poisson or negative binomial random-effects regression (extending to a more general hidden Markov model in the event of poor fit of the simpler models). Specifically, we will test the hypothesis that the underlying event rate per unit time is the same in the treatment and sham eyes. As a secondary analysis, we will analyze the time to first adverse event in each group using Cox proportional hazards regression (using baseline medical history as well as time since last treatment as covariates). We emphasize that while the statistical fit may be informative, decisions about drug safety (or trial continuation) will not be based solely on statistical criteria.

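### The any-ocular-event, time-to-first-event and pooled-rate summaries have no onset window, so expected post-operative events in both eyes may dilute a later difference due to the implant

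*SAP*

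**What the plan says.** **The summaries.** SAP 7.7.2.2 pools events into four categories, one of which is any ocular adverse event, and states: "The proportion of subjects with these events will be compared between the arms". It also applies Poisson regression to overall event rates with repeat events counted. SAP 7.5.2.7 tests equality of event rates in treated and sham eyes by Poisson or negative binomial regression and then, as a secondary analysis: "we will analyze the time to first adverse event in each group". SAP 7.7 adds a McNemar comparison of incidence. None of these specifies an onset period, a landmark, or separate handling of expected surgical events.

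**What feeds them.** Protocol 4.6.1 has the conjunctiva of both eyes opened and sutured. For the sham eye the step reads: "Perform an inferior limbal conjunctiva peritomy under microscopic visualization using scissors". The sham eye also has a block or a skin puncture, and subconjunctival dexamethasone. Only the implant eye has a sclerotomy and a device. Protocol 4.1 foresees irritation: "Participants may experience a transient red eye from superficial bleeding and itching or a foreign body sensation in the corner of the eye". It expects such effects generally to clear within two weeks. It also says that "all adverse events will be collected regardless of severity or potential relationship to the implant, CNTF, or surgical procedure". Table 1 schedules nine post-operative adverse event assessments. Three of them (day 1, week 1, month 1) fall in the first month, and six cover the next 35 months.

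**The concern.** An eye that has a mild post-operative event has already reached the any-event endpoint and has used up its first event. Neither summary can then register a later event in that eye. If post-operative events are common and similar in the two eyes, the comparison mostly reflects surgery that both eyes had. The question that needs up to 36 months of follow-up, whether sustained CNTF release or the retained device causes harm later, is then answered with less power than the data allow. Replacing Fisher's test with McNemar's or a clustered model does not help, because the loss comes from the definition of the endpoint.

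**Working it through.** **The plan's own figure.** The documents give no adverse event rate and no adverse event power. Their only power statement concerns cone spacing: "80% power to detect an effect size of 0.084 arcminutes over two years", with an "expected standard deviation of the difference in the total change in cone spacing after two years of approximately 0.11". The standardized effect is 0.084/0.11 = 0.764. A two-sided paired t-test at 0.05 needs 16 people (power 81.4%), and 17 give 84.0%. That agrees with the SAP's 17 to within one person, and 17/0.85 = 20. I use 20 (SAP 3.1.5) and 30 (Protocol section 4, approximate); Protocol 6.1 says 10, where power would be lower still. The test level follows SAP 3.1.1: "Results will be judged significant using a two-tailed α of 0.05".

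**Dilution.** Let e be the chance of an early (post-operative) event, assumed equal in both eyes. Let L1 and L0 be the chances of a late event in the implant and sham eye, independent of early events. All three are assumptions.

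- Any event, implant eye: 1 − (1 − e)(1 − L1)
- Any event, sham eye: 1 − (1 − e)(1 − L0)
- Difference: (1 − e)(L1 − L0)

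The late difference shrinks by the factor (1 − e). With L1 = 0.40, L0 = 0.05 and e = 0.5, the any-event proportions are 70.0% and 52.5%, so a 35-point difference becomes 17.5 points.

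**Power of exact McNemar.** Assume that early status is identical in the two eyes for half of the participants and independent for the rest.

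- Neither eye early: N = 0.5(1 − e) + 0.5(1 − e)²
- One given eye only: O = 0.5e(1 − e)
- Implant eye only has an event: p10 = (1 − L0)(N·L1 + O)
- Sham eye only has an event: p01 = (1 − L1)(N·L0 + O)

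At e = 0.5: N = 0.375 and O = 0.125, so p10 = 0.95 × 0.275 = 0.261 and p01 = 0.60 × 0.144 = 0.086. Summing the exact two-sided test over the binomial distribution of discordant pairs gives, for L1 = 40% and L0 = 5%:

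| Early rate e | n = 20 | n = 30 |
|---|---|---|
| 0 (late events only) | 64% | 88% |
| 10% | 49% | 74% |
| 30% | 27% | 47% |
| 50% | 14% | 26% |
| 70% | 4% | 11% |
| 90% | 0.1% | 0.5% |

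**Sensitivity to the late contrast.** For late events alone, power is 20% (n = 20) and 44% (n = 30) at 25% v 5%, and 9% and 25% at 20% v 5%.

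**Fisher's test, as written in 7.7.2.2.** With late events in 40% v 10%, n = 20 and early events independent between eyes, power falls from 49% (e = 0) to 10% (e = 0.5) and about 1% (e = 0.9).

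**Time to first event.** With the same 40% v 10%, early onsets spread over days 0 to 14, late onsets exponential to 36 months, and a log-rank test as a stand-in for the Cox model, n = 20 power is 62%, 10% and 3% at e = 0, 0.5 and 0.9. Days 0 to 14 hold 80% of first events at e = 0.5 and 97% at e = 0.9.

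**Pooled rate with repeat events.** Late risks of 40% and 10% correspond to mean counts −ln 0.6 = 0.511 and −ln 0.9 = 0.105, a ratio of 4.85. Adding a mean of e early events per eye gives (0.511 + e)/(0.105 + e): 1.67 at e = 0.5 and 1.40 at e = 0.9. Power at n = 20 is 56% for late events only, and 19% and 4% for all events pooled.

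**The case against.** **No rate is given.** A reader might infer that the any-event endpoint will be nearly saturated within days and so cannot show later harm. The documents do not support that. Protocol 4.1 says only that participants may have these symptoms, and Protocol 8.1 calls the surgical risks very small. At early rates of 10% to 30% the summaries are weakened, not blind. This objection stands, and the claim is limited accordingly.

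**The safety plan is wider than these summaries.** A reader might also infer that the SAP would miss late events altogether. It would not:

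- SAP 7.7.2.2 has a separate serious ocular category.
- SAP 7.7.2.1 compares listed events one by one, including cataract and retinal detachment.
- SAP 7.5.2.7 puts event rates first and makes time to first event secondary.
- SAP 7.4 and 7.5.2 treat the cone, acuity, field, layer-thickness and ERG results as safety evidence too, and do not rest the safety judgment on tests alone.

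These are real but partial safeguards. The pooled rate has no period split. The serious list includes surgical infection and bleeding, which can arise early. The listed events do not name extrusion, peri-implant fibrosis or choroidal neovascularization, all of which Protocol 4.1 names.

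**A split may gain little.** At 20% v 5%, power is low even for late events alone, and SAP 7.4 already concedes that the trial is not powered for unlikely events. This also stands: the split removes a dilution but does not make a small trial sensitive.

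**Early events matter.** It is tempting to judge the implant on later events only. Because only the implant eye has a sclerotomy and device, early infection, bleeding, detachment or extrusion can be implant-specific, and the staggered enrolment in Protocol section 4 relies on the day-1, week-1 and month-1 findings. The early period must keep its standing.

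**Conclusion.** The point holds as a cheap improvement. The any-ocular-event proportion, time to first event and the pooled rate do not separate the post-operative period from later follow-up, although both eyes have conjunctival surgery and all events count. They may be dominated by expected post-operative events and so have reduced power to show later implant harm.

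The dilution factor (1 − e) follows by arithmetic if early risk is equal in the two eyes and independent of late risk. Its size is conditional, because every event rate used here is an assumption. The loss is modest at an early rate of 10% and nearly total at 90%, and the gain from separating the periods is substantial only if the late contrast is large. Nothing here shows that the endpoint will saturate, or that the wider safety plan is unable to detect late harm.

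**What to change.** Keep the planned whole-study comparisons. In SAP 7.7.2.2 and 7.5.2.7, prespecify in addition:

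1. A comparison of ocular adverse events by onset period (surgery through the 1-month visit; after the 1-month visit to month 36), applied both to the proportions and to the Poisson or negative binomial rates.
2. A landmark analysis of time to first ocular event starting at the 1-month visit. It includes every eye still followed, whatever its earlier events, and counts only onsets after that visit.
3. A statement that both periods are reported with equal standing.

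The cost is SAP wording and a few table columns, using recorded onset dates; no visit or procedure changes. The downside is a cut-point that some post-operative events may cross. For instance, the post-operative drop schedule in Protocol 4.6.3 runs 5 + 7 + 7 + 7 + 7 = 33 days from the day after surgery, which can extend past the 1-month visit. The SAP should acknowledge this when it defines the periods.
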